We believe that losing a client to suicide at a site could change the responses that participants give at a given Step of the study. Therefore, at the beginning of each step, we will ask if a client at the site died by suicide since our last assessment and if so, was it someone in the target group from which we are recruiting client participants. (We may well learn from other sources that our participant died by suicide (i.e., when they do not respond to outcome assessments), but the purpose of this procedure is to be aware of a potential confounder of study results – that is, that a suicide at the site might change suicide-related study results at that Step. Of course, if we learn a study participant then we will submit an adverse event report to the IRB.)

For the Administrative Supplement,

5.3 Data sources. For all types of data that you will access or collect for this research: Identify whether you are obtaining the data from the subjects (or subjects' specimens) or whether you are obtaining the data from some other source (and identify the source).

If you have already provided this information in Question 5.1, you do not need to repeat the information here.

Participant questionnaires, medical record (plus verbal consultation with counselor, if needed)

For the Administrative Supplement,

5.4 Retrospective/prospective. For all types of data and specimens that you will access or collect for this research:

Describe which data are:

- Retrospective (i.e., exist at the time when you submit this application)
- Prospective (i.e., do not yet exist at the time when you submit this application)
- Both retrospective and prospective (for example, past and future school records)

Retrospective. (NOTE: Their medical history in the records preceeds study consent; but their records are obtained after consent.)

5.5 Identifiability of data and specimens. Answer these questions carefully and completely. This will allow HSD to accurately determine the type of review that is required and to assist you in identifying relevant compliance requirements. Review the following definitions before answering the questions:

Access means to view or perceive data, but not to possess or record it. See, in contrast, the definition of "obtain".

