Primary outcome analyses. In the proposed stepped wedge design, 15 addiction treatment sites that initially provide TAU (Step 1) will be randomized to implement PARS beginning at one of five ensuing steps (Steps 2-6), 3 sites at a time. Participants recruited at each step will be assessed at points: baseline, post-treatment (information and attitudes only), 1, 3, and 6 months. The primary outcome analyses will be intent-to-treat analyses that include all participants, including those with incomplete follow-up data. The primary outcomes will be 1) knowledge about suicide, 2) maladaptive attitudes towards suicide, and 3) help-seeking behaviors. Each outcome will be evaluated in a separate generalized linear mixed model (GLMM)⁶⁰ to evaluate the effect of PARS program vs. Treatment As Usual on change in each outcome over time. The GLMM approach accounts for within-individual and between-group variance and is well-suited for the analyses of multisite, repeated measures data. A logit link function will be used to model dichotomous outcomes and a Gaussian link function when the outcome is relatively normally distributed.

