*The following regression equation depicts the basic model for each outcome: $OUTCOME_{tis} = b_0 + b_1 STEP2_{is} + b_2 STEP3_{is} + b_3 STEP4_{is} + b_4 STEP5_{is} + b_5 STEP6_{is} + b_6 SETTING_{is} + b_7 PARS_{is} + b_8 MONTH1_{tis} + b_9 MONTH3_{tis} + b_{10} MONTH6_{tis} + b_{11} (PARS_{is} * MONTH1_{tis}) + b_{12} (PARS_{is} * MONTH3_{tis}) + b_{13} (PARS_{is} * MONTH6_{tis}) + u_{0s} + r_{0is} + e_{tis}$, where t indexes the assessment, i indexes the individual, and s indexes the site. In this model, each outcome is regressed on Step, Setting (Rural vs. Urban), Treatment (PARS vs. TAU), Time (in months), and the Treatment by Time interaction. The effect of Step will be coded into contrasts of Step 1 against each subsequent step (i.e., Step 2 vs 1, Step 3 vs 1, etc.). The effect of Time will be coded into contrasts of baseline (BL) against each post-baseline assessment (i.e., BL vs. 1 month, BL vs. 3, BL vs. 6 months). To account for the cluster-randomized design, a random effect for site (u_{0s}) will be included to model the correlation of individuals from the same site. To account for the repeated assessments, a random effect for participant (r_{0is}) will be included to model the correlation of observations within the same individual. The statistical test of the treatment effect will be the magnitude and statistical significance of the Treatment by Time interactions. Comparable analyses will be used for exploratory aims with suicidality and substance use.*

Since this study will be carried out at 15 sites, there is the potential for site-specific effects. We anticipate intervention effects to be comparable across all clinics since they are all serving similar client populations and have counselors with comparable levels of experience and training. To verify that treatment effects are comparable across site, preliminary outcome analyses will incorporate indicator variables for site and their interactions with the treatment effects. A likelihood ratio test will be used to compare the models with and without site-specific effects. If the likelihood ratio tests reveal differences in treatment effect by site, these

site-specific parameters will be retained in the final analyses, otherwise they will be excluded.

Secondary Analyses

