Dose Response Analyses. Exploratory analyses will evaluate whether Time (i.e., number of steps) in the intervention phase is associated with improved outcomes in successive steps. The following regression equation depicts the basic dose response model for each outcome: $OUTCOME_{t>0, is} = b_0 + b_1 BL_OUTCOME_{is} + b_2 TAU_TIME_{is} + b_3 PARS_TIME_{is} + u_{0s} + r_{0is} + e_{tis}$, where t indexes the assessment, i indexes the individual, and s indexes the site. In this model, Time will be centered at the beginning of the intervention phase, such that Time = 0 will correspond to the step in which PARS was implemented at a particular site. Time will be coded as a piecewise linear function representing two phases: 1) the TAU phase: the change over time in outcomes during the control period and the 2) PARS phase: a “deflection” term representing the change in slope from the TAU phase following the implementation of PARS. To account for the cluster-randomized design, a random effect for site (u_{0s}) will be included to model the correlation of individuals from the same site. To account for the repeated assessments, a random effect for participant (r_{0is}) will be included to model the correlation of observations within the same individual. The statistical test of the dose-response effect will be the magnitude and statistical significance of the slope of Time during the intervention period.

Power Analysis. We base our power analysis on a stepped wedge design³⁵ evaluating the difference in the rate of help-seeking behavior at month 1 (post-intervention) among those receiving PARS vs. TAU. Based on our pilot study of PARS, we anticipate a 15.6% baseline rate of help seeking behavior, which we expect to increase to 28.1% at post-intervention (1-month) follow-up. Based on the proposed stepped wedge design in which 10 individuals are recruited per site in each of the 6 steps ($N = 900$), we will have 89% power to detect the 12.5% difference in the rate of help-seeking behavior. Assuming 25% fewer participants ($N = 675$, 7.5 individuals per site per step), due to under-recruitment and/or attrition, there will still be 80% power to detect an intervention effect. This represents a conservative estimate of statistical power as the full longitudinal model will leverage data from all participants, including those with incomplete follow-up data.

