Missing data. Missing data may occur in several ways. First, missing data may occur due to item non-response. When missing data is limited to only a few items on a measure, we will prorate total scores for a measure by taking an average score on the measure and multiplying it by the total number of items in the scale. Missing data can also occur from attrition due to missed assessments or dropout from the study. Prior to performing any outcome analyses, we will evaluate the amount, reasons, and patterns of missing data. If the

Figure 2

reason for missing data is not related to the outcome of interest, then the missing data are considered to be missing completely at random and complete case analysis will still generate unbiased estimates.⁶⁵ A multiple imputation using chained equations approach will be utilized to address missing data, with the final results calculated as a pooled average across 10 multiply-imputed data sets using Rubin's methodology.⁶⁶ We will conduct sensitivity analyses to compare estimates of treatment effects with and without multiple imputation to assess the effect of missing data on statistical inference.

C.8 Dissemination Plan

[name] will lead a PARS Advisory Group as he did in the R21 study including [name] and [name] as well as [name], and three agency heads: [REDACTED] (see Letters of Support for their willingness to participate). The Advisory Group will meet periodically throughout the study and then will have multiple meetings in Year 5 to develop a dissemination plan if PARS is effective.

C.9. Time Line

	Year 1		Year 2		Year 3		Year 4		Year 5	
	0-6	7-12	0-6	7-12	0-6	7-12	0-6	7-12	0-6	7-12
Hire and train personnel	[REDACTED]									
Organize study with partners	[REDACTED]									
Step 1 (baseline for all sites)		[REDACTED]								
Step 2 (3 new sites start PARS)			[REDACTED]							
Step 3 (3 new sites start PARS)				[REDACTED]						
Step 4 (3 new sites start PARS)					[REDACTED]					
Step 5 (3 new sites start PARS)						[REDACTED]				
Step 6 (3 new sites start PARS)							[REDACTED]			
Follow-up assessments		[REDACTED]						[REDACTED]		
Conduct outcome analysis								[REDACTED]		
Disseminate study results									[REDACTED]	

C.10. Study Limitations

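### The site random intercept drops out of the tested PARS x MONTH contrast, so the primary standard error assumes clients' changes are independent within site and session

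*SAP*

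**What the plan says.** SAP C.7 (Primary outcome analyses) fits one mixed model per primary outcome: knowledge, maladaptive attitudes and help-seeking. The fixed effects are step, rural/urban setting, PARS, month (1, 3 and 6 against baseline) and PARS x MONTH. There are two random effects, both intercepts:

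- Site: "To account for the cluster-randomized design, a random effect for site (u_{0s}) will be included".
- Participant: "a random effect for participant (r_{0is}) will be included to model the correlation of observations within the same individual".

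The test is defined as follows: "The statistical test of the treatment effect will be the magnitude and statistical significance of the Treatment by Time interactions". On link functions: "A logit link function will be used to model dichotomous outcomes", with a Gaussian form for roughly normal outcomes.

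One site check is planned: "preliminary outcome analyses will incorporate indicator variables for site and their interactions with the treatment effects". A likelihood-ratio test decides whether those terms stay.

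For missing data, the SAP has "the final results calculated as a pooled average across 10 multiply-imputed data sets".

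For the primary model the SAP gives no random effect for change at site or site-step level, no cluster-robust standard error, no permutation test and no small-sample degrees of freedom. Robust standard errors appear only in the mediation model, for non-normality.

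**The concern.** A random intercept allows for clustering of outcome levels. The tested coefficients are differences in change from baseline, and a constant added to every visit of a client or site does not alter a change. The term offered as protection against clustering therefore acts on the PARS main effect, which is not the test.

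What matters for the test is whether clients' changes correlate. The design gives a reason not to assume that they do not. One IOP group per site is studied, each step brings new clients (Protocol 1.6), and those clients share a single session built partly on group discussion (Protocol 5.1), delivered by that site's counselor. If changes do correlate, intervals for all three primary outcomes are too narrow and the nominal 5% test rejects too often.

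**Working it through.** **Inputs.** From the SAP: 15 sites, 6 steps, 3 sites crossing over at each of Steps 2-6, and "10 individuals are recruited per site in each of the 6 steps" (Power Analysis). This gives 45 PARS and 45 TAU site-step cells, or 450 clients per condition. The SAP also allows for 7.5 per cell. Assumed, because not stated: two-sided alpha of 0.05 and every ICC of change.

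**1. The plan's own power figure.** The standard stepped-wedge variance formula, for 15.6% vs 28.1% at month 1 with a site intercept and an assumed site ICC of 0.005, gives about 89% power at 10 per cell and 80% at 7.5. This matches the SAP. The calculation is for a post-only comparison, and its ICC concerns levels. It says nothing about correlation of change.

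**2. Cancellation.** I built the SAP model on 15 x 6 x 10 clients x 4 visits, with residual variance 0.5 and participant variance 0.5.

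| Site variance | SE of PARS x MONTH1 | SE of PARS main effect |
|---|---|---|
| 0 | 0.0667 | 0.083 |
| 0.05 | 0.0667 | 0.098 |
| 0.5 | 0.0667 | 0.102 |
| 5 | 0.0667 | 0.103 |

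The constant 0.0667 is sqrt(2 x 0.5 x (1/450 + 1/450)), the standard error for two samples of independent change scores. With 20% of follow-up visits missing (assumed) it is 0.07165 to 0.07166 over the same range of site variance. In a logit working model it is 0.2483 at every site variance tried with complete data, and 0.2669 to 0.2670 with 25% missing.

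**3. True against nominal variance of the month-1 contrast.** Each cell has weight +1/45 (PARS) or -1/45 (TAU).

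- Sum of squared cell weights: 90/45² = 0.04444.
- Net site weights by group are +4, +2, 0, -2 and -4 (each /45), with 3 sites per group. Sum of squares: 3 x (16+4+0+4+16)/45² = 120/2025 = 0.05926, which is 1.333 times 0.04444.
- Site-step ICC, n per cell: ratio = 1 + (n-1) x ICC. That is 1 + 9 x ICC at n = 10 and 1 + 6.5 x ICC at n = 7.5.
- Site-only ICC, n = 10: ratio = 1 + (13.33-1) x ICC = 1 + 12.33 x ICC.
- Type I error = 2 x (1 - Phi(1.96/sqrt(ratio))).

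| Assumed ICC of change | Clients per cell | Variance ratio | Type I error |
|---|---|---|---|
| zero | any | 1.00 | 5.0% |
| site-step 0.005 | 10 | 1.045 | 5.5% |
| site-step 0.01 | 10 | 1.09 | 6.1% |
| site-step 0.02 | 10 | 1.18 | 7.1% |
| site-step 0.05 | 10 | 1.45 | 10.4% |
| site-only 0.02 | 10 | 1.25 | 7.9% |
| site-only 0.05 | 10 | 1.62 | 12.3% |
| site-step 0.02 | 7.5 | 1.13 | 6.5% |
| site-step 0.05 | 7.5 | 1.325 | 8.9% |

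Simulation of the linear model (20,000 trials per setting, 10 per cell) agrees: 5.5, 6.0, 7.2 and 10.2% for the four site-step rows, and 8.0 and 12.6% for site-only. In the same trials a site-level robust test (CR2, t with 14 df) rejected 4.9-5.2% of the time.

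**4. Binary help-seeking.** A four-visit logit mixed model was simulated at a 15.6% rate, without the rural/urban term (2,000 trials per setting, Monte Carlo error about 0.5 points). With a site-step SD of logit change of 0, 0.25, 0.5 and 0.75, rejection was 5.9, 4.6, 6.2-7.2 and 8.7%. Site-only SD 0.5 gave 7.4%.

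**5. The likelihood-ratio check.** On month-1 change, with two plausible codings of the site terms (2,000 trials), it flagged 80-94% of trials at site-only ICC 0.05. It flagged only 14-19% and 31-47% at site-step ICC 0.02 and 0.05. With a third coding, by site, PARS and month (3,000 trials), it missed site-step ICC 0.02 in 77% of trials, and the primary test rejected in 7.6% of those.

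**The case against.** **The ICC of change may be zero or tiny.** This stands: the planned test would then be valid or nearly so. The value of about 0.005 that reproduces the SAP's power concerns levels, so it neither supports nor excludes a given value for change. The 0.05 rows have no basis in the documents and only show sensitivity.

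**Correlated change is less likely under a no-effect null.** Protocol 5.1 says no partner IOP now has a session focused on suicide prevention, and nothing suggests that a session on grief or depression would move suicide knowledge in step. This weakens the type I figures. Sessions may still differ in how well PARS works, which affects interval width.

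**A reader might cite Protocol 5.2 as evidence of clustering**, where the investigators believe that "losing a client to suicide at a site could change the responses that participants give at a given Step of the study". It does not support the point. The question is asked at the start of a step about deaths since the previous assessment, so the event precedes that step's baseline. It would mainly shift baseline and follow-up together, and the contrast removes that.

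**The figures shrink on the plan's own terms.** At 7.5 per cell they are lower, as shown. With 20% of month-1 values imputed, a simulation of the planned linear test gave about 5.5, 6.6 and 9.1% at site-step ICC 0, 0.02 and 0.05. For help-seeking, inflation is hard to separate from simulation error below an SD of 0.75.

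**The site check is a safeguard.** In part it is, for site-level clustering. It has no site-step term, acts only when significant and keeps client-level standard errors.

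**A reader might infer that the stated 89% power is lost.** That figure is not for the tested contrast. For a 12.5-point difference in change (assumed within-person correlation 0.5, normal approximation, 10 per cell), power is 99.8% at zero ICC and 91.9% with ICC 0.05 at both levels.

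**Conclusion.** The point holds as a gap in the plan's stated protection, with a conditional effect on error rates. It is certain from the SAP's equation that the site intercept does not reach the tested coefficients, and that no cluster-valid test is pre-specified for them. Whether this matters depends on an ICC of change that the documents do not give. For Gaussian outcomes with 10 completers per cell, type I error runs from 5% at zero to about 7-8% at ICC 0.02 and 10-12% at 0.05, and is lower with fewer completers. For binary help-seeking the inflation is probably small, so the concern bears mainly on knowledge and attitudes, if these are modelled as Gaussian.

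A reader might infer that the primary test is invalid or that false positives are to be expected. The documents do not support that. They support only that independence of change is assumed silently while the SAP says clustering is accounted for. This should be fixed; confidence in the practical size is medium.

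**What to change.** Keep the mean model. For all three primary outcomes, pre-specify in SAP C.7:

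- A site-level cluster-robust standard error for each PARS x MONTH coefficient, with a small-sample correction for 15 sites: CR2 with t(14) or Satterthwaite degrees of freedom.
- The exact bias-corrected sandwich estimator for the logit model. The simulations used a CR2-type site-level correction (4.4-5.5% rejection), but the SAP must name its own.
- Computation in each of the 10 imputed data sets, pooled by Rubin's rules with small-sample degrees of freedom.
- Reporting of the estimated ICC of change.
- A statement that the likelihood-ratio test does not decide whether clustering is handled.

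A permutation test over the actual site allocation could be added as a sensitivity analysis.

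**Cost.** SAP wording only; trial conduct is unchanged. With complete data, intervals are about 8% wider at zero ICC, and about 12, 17 and 30% wider at site-step ICC 0.01, 0.02 and 0.05. For binary help-seeking they are about 9% wider at zero. Under imputation the test may be somewhat conservative: with 20% of month-1 values missing, simulated rejection was 2.9% at zero ICC, 2.5% at 0.02 and 4.6% at 0.05 (1,000 trials each).
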